6.2.2. Study Parts A and B: Baseline/Day 1 Assessments

The following evaluations are to be completed at the Day 1 visit in-clinic. The investigator must have confirmed eligibility before proceeding with randomization. If the screening and Day 1 visits occur on the same day, no procedures need to be repeated. Participants must complete the following assessments before being administered study treatment, unless otherwise stated:

- Complete symptom-directed physical examination including vital signs (heart rate, temperature, blood pressure, SpO₂)
- Perform 12-lead electrocardiogram (ECG)
- Perform FEV₁ (predose and 10 minutes postdose)

Repeat of FEV₁ should be performed 30 minutes postdose if there is $> 15\%$ reduction in FEV₁ at 10 minutes postdose compared with the same day predose FEV₁. FEV₁ assessment may also be performed if there is a clinical concern of bronchospasm

- Perform chest x-ray
- Complete daily adapted FLU-PRO[©] questionnaire
- Safety laboratory samples will be collected for the following analyses:

Hematology

Coagulation

Chemistry

- Obtain nasopharyngeal and oropharyngeal swabs, and saliva samples for SARS-CoV-2 quantitative reverse transcriptase polymerase chain reaction (RT-qPCR) testing and possible viral resistance testing
- Sparse plasma PK assessment: end of nebulization **CCI**
[REDACTED]
[REDACTED]
[REDACTED]
[REDACTED]
- Review AEs and concomitant medications
- Inhaled Remdesivir for Injection formulation administration:

Inhaled Remdesivir for Injection formulation will be administered to participants at the site under close supervision.

Healthcare professionals administering inhaled Remdesivir for Injection formulation should have the appropriate medication available for immediate use in case of hypersensitivity. The participant should be treated according to the standard of care (SOC) for management of hypersensitivity reaction. After dose administration, monitoring should be done as follows:

- Approximately 30 minutes post dose administration, participants should be observed, and vital signs should be performed prior to discharge

6.3. Study Parts A and B: Daily Study Assessments (Days 2-5)

The following evaluations are to be completed daily and prior to study treatment administration from Days 2-5 in-clinic, unless otherwise stated:

- Complete symptom-directed physical examination including vital signs (heart rate, temperature, blood pressure, SpO₂)
- Complete daily adapted FLU-PRO[©] questionnaire
- Safety laboratory samples (Days 3 and 5)

- Obtain nasopharyngeal, oropharyngeal swabs, and saliva samples for SARS-CoV-2 RT-qPCR testing and possible viral resistance testing
- Perform FEV₁ (predose and 10 minutes postdose)

Repeat of FEV₁ should be performed 30 minutes postdose if there is > 15% reduction in FEV₁ at 10 minutes postdose compared with the same day predose FEV₁. FEV₁ assessment may also be performed if there is a clinical concern of bronchospasm

- Sparse plasma PK assessment: predose and end of nebulization (Day 3)

- Review AEs and concomitant medications
- Inhaled Remdesivir for Injection formulation administration:

Inhaled Remdesivir for Injection formulation will be administered to participants at the site under close supervision. Healthcare professionals administering inhaled Remdesivir for Injection formulation should have the appropriate medication available for immediate use in case of hypersensitivity. The participant should be treated according to the SOC for management of hypersensitivity reaction. After dose administration, monitoring should be done as follows:

Approximately 30 minutes post dose administration, participants should be observed, and vital signs should be performed prior to discharge

6.4. Study Parts A and B: Follow-Up Assessments (Days 7 and 14)

The following evaluations are to be completed on Days 7 and 14 (\pm 3 days) in-clinic:

- Complete symptom-directed physical examination including vital signs (heart rate, temperature, blood pressure, SpO₂)
- Complete daily adapted FLU-PRO[©] questionnaire
- Safety laboratory samples
- Obtain nasopharyngeal, oropharyngeal swabs, and saliva samples for SARS-CoV-2 RT-qPCR testing and possible viral resistance testing
- Single PK assessment (Day 7)
- Review AEs and concomitant medications

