Appendix 3. Study Procedures Tables

Appendix Table 1. Study Parts A and B: Study Procedures Table

Schedule of Assessments	Screening	TREATMENT PERIOD					FOLLOW-UP PERIOD		
		Day 1 ^a	Day 2	Day 3	Day 4	Day 5	Day 7	Day 14 (± 3 days)	Day 28 ^b (± 5 days)
Obtain Informed Consent	X								
Inclusion/Exclusion Criteria	X								
Medical History	X								
Documentation of SARS-CoV-2	X								
ECG ^c		X							
Complete or Symptom-Directed Physical Examination	X	X	X	X	X	X	X	X	
Body Weight	X								
Height	X								
Vital Signs (Heart Rate, Temperature, Blood Pressure, SpO ₂)	X	X	X	X	X	X	X	X	
Completion of Daily Adapted FLU-PRO [©] Questionnaire ^d		X	X	X	X	X	X	X	
Chest X-Ray ^e		X							
FEV ₁		X	X	X	X	X			
Safety Laboratory Assessments (Hematology, Chemistry, Coagulation)		X		X		X	X	X	
Pregnancy Test (Urine)	X								
Serum FSH Test ^f	X								
Nasopharyngeal and Oropharyngeal Swabs and Saliva Samples for SARS-CoV-2 RT-qPCR Testing and Possible Viral Resistance Testing		X	X	X	X	X	X	X	
Sparse Plasma PK Assessments ^g		X		X					

ECG = electrocardiogram; FEV₁ = forced expiratory volume in the first second of expiration; FLU-PRO[®] = InFLUenza Patient-Reported Outcome; FSH = follicle-stimulating hormone; PCR = polymerase chain reaction; PK = pharmacokinetic(s); RT-qPCR = quantitative reverse transcriptase polymerase chain reaction; RDV = (remdesivir, GS 5734TM); SARS-CoV-2 = severe acute respiratory syndrome coronavirus 2; SpO₂ = oxygen saturation as measured by pulse oximetry

- a If the screening and Day 1 visits occur on the same day, no procedures need to be repeated.
- b Day 28 assessments may be completed by telephone.
- c ECG will not be required at screening. However, ECG should be performed prior to dosing on Day 1. If subject randomizes and doses on the same day as screening, then ECG will be done at screening.
- d Adapted FLU PRO[®] questionnaire is to be completed daily (Days 1-14).
- e Chest x-ray will be performed at Day 1. If screening visit and Day 1 are the same day, chest x-ray does not need to be repeated if completed as SOC < 2 days before screening.
- f Serum FSH test: Childbearing female participants who are not postmenopausal (see [Appendix 5](#) who do not wish to follow protocol defined contraception will need a serum FSH test (FSH test is required for women who are < 54 years old and have stopped menstruating for ≥ 12 months but do not have documentation of ovarian hormonal failure)

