3.8.2. Analysis Visit Windows

Participant visits might not occur on protocol-specified days. Therefore, for the purpose of analysis, observations will be assigned to analysis windows.

The analysis windows for vital signs and SpO₂ are provided in [Table 3-1](#) (Parts A and B) and [Table 3-2](#) (Part C).

Table 3-1. Analysis Visit Windows for Vital Signs, and SpO₂ in Parts A and B

Nominal Visit	Nominal Study Day	Visit Window Study Day	
		Lower Limit	Upper Limit
Baseline	1	(none)	1 (pre dose)*
Day 1	1	1 (post dose)	1
Day 2	2	2	2
Day 3	3	3	3
Day 4	4	4	4
Day 5	5	5	6
Day 7	7	7	9
Day 14	14	10	21
Post Day 14	28	22	(None)

* For Baseline, the upper limit includes values collected at or prior to the first dose date/time.

Table 3-2. Analysis Visit Windows for Vital Signs and SpO₂ in Part C

Nominal Visit	Nominal Study Day	Visit Window Study Day	
		Lower Limit	Upper Limit
Baseline	1	(none)	1 (pre dose)*
Day 1	1	1 (post dose)	1
Day 3	3	2	4
Day 5	5	5	6
Day 7	7	7	13
Post Day 7	14	14	(None)

* For Baseline, the upper limit includes values collected at or prior to the first dose date/time.

The analysis windows for SARS-CoV-2 viral load are provided in [Table 3-3](#) (Parts A and B) and [Table 3-4](#) (Part C).

Table 3-3. Analysis Visit Windows for SARS-CoV-2 Viral Load in Parts A and B

Nominal Visit	Nominal Study Day	Visit Window Study Day	
		Lower Limit	Upper Limit
Baseline	1	(none)	1 (pre dose)*
Day 2	2	1 (post dose)	2
Day 3	3	3	3
Day 4	4	4	4
Day 5	5	5	6
Day 7	7	7	9
Day 14	14	10	21
Post Day 14	28	22	(None)

* For Baseline, the upper limit includes values collected at or prior to the first dose date/time.

Table 3-4. Analysis Visit Windows for SARS-CoV-2 Viral Load in Part C

Nominal Visit	Nominal Study Day	Visit Window Study Day	
		Lower Limit	Upper Limit
Baseline	1	(none)	1 (pre dose)*
Day 3	3	1 (post dose)	4
Day 5	5	5	6
Day 7	7	7	9
Post Day 7	14	10	(None)

* For Baseline, the upper limit includes values collected at or prior to the first dose date/time.

The analysis windows for hematology, coagulation, and chemistry laboratory tests are provided in [Table 3-5](#) (Parts A and B) and [Table 3-6](#) (Part C).

Table 3-5. Analysis Visit Windows for Hematology, Coagulation, and Chemistry Laboratory Tests in Parts A and B

Nominal Visit	Nominal Study Day	Visit Window Study Day	
		Lower Limit	Upper Limit
Baseline	1	(none)	1 (pre dose)*
Day 3	3	1 (post dose)	4
Day 5	5	5	6
Day 7	7	7	9
Day 14	14	10	21
Post Day 14**	28	22	(None)

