 - The record closest to the nominal day for that visit will be selected with the exception of viral load in which the latest record will be selected.

- If there are 2 records that are equidistant from the nominal day, the later day will be selected.
- If there is more than 1 record on the selected day, values will be selected for analysis as follows:
 - For viral load, if there is more than 1 record on the selected day, the latest value will be selected. If there are multiple records with the same time or no time recorded on the same day, the geometric mean value (copies/mL) will be taken.
 - For FLU-PRO questionnaire response, the worst severity will be taken if there is more than 1 record on the selected day. If the severity is the same, the latest record will be selected.
 - For other parameters, if there is more than 1 record on the selected day, the average will be taken for continuous data and the worst severity will be taken for categorical data, unless otherwise specified.
- For postbaseline values of PCR negative confirmation (separately by sample types):
 - Use all available data to derive negative confirmation except if there are multiple records on the same day, worst value will be used for negative confirmation for that day
 - The record closest to the nominal day for that visit will be selected.
 - If there are 2 records that are equidistant from the nominal day, the later record will be selected.
- For postbaseline values PCR for DAVG calculation:
 - All values from different days within an analysis window will be used for DAVG calculation.
 - If there is more than 1 record on a study day, the latest value will be selected. If there are multiple records with the same time or no time recorded on the same day, the geometric mean value (copies/mL) will be taken.

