6.1.1. Definition of the Primary Efficacy Endpoint

The primary endpoint of the study is time-weighted average change from baseline to Study Day 7 (DAVG₇) in SARS-CoV-2 viral load (log₁₀ copies/mL). The DAVG₇ in SARS-CoV-2 viral load is defined as the time-weighted average between the first postbaseline value through the last available value up to Study Day 7 minus the baseline value in SARS-CoV-2 viral load. DAVG₇ is calculated using the trapezoidal rule and the area-under-the-curve (AUC) concept as follows:

$$DAVG_7 = \frac{AUC_{t_1-t_7}}{(t_7 - t_1)} - Y_0$$

The AUC between t_1 and t_n in a time (i.e., study day) versus SARS-CoV-2 viral load plot is calculated as follows:

$$AUC_{t_1-t_n} = \sum_{i=1 \text{ to } (n-1)} \frac{1}{2} (Y_i + Y_{i+1}) \times (t_{i+1} - t_i)$$

Where Y_i is the SARS-CoV-2 viral load at time t_i , t_1 is the first postbaseline time, and Y_0 is the baseline SARS-CoV-2 viral load.

For participant with SARS-CoV-2 viral load data only available up to Day x ($x < 7$), the

$$DAVG_7 \text{ is defined as } DAVG_7 = \frac{AUC_{t_1-t_x}}{(t_x - t_1)} - Y_0$$

If there is no post-baseline data, then the participant will be excluded from the analysis. If there is one post-baseline data value Y_i , $DAVG_7 = Y_i - Y_0$.

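### The Parts A and B Day 7 visit window is ambiguous between Protocol 6.4 and Appendix Table 1, and the SAP's latest-record rule for viral load lets a Day 6 swab displace an on-schedule Day 5 swab

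*Protocol*

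**What the plan says.** **Visit timing, Parts A and B.** Protocol 6.4 requires the follow-up evaluations to be "completed on Days 7 and 14 (\pm 3 days) in-clinic". The ± 3 days is written once, after both days. In Appendix Table 1 of the protocol the column headings run "Day 7 Day 14 (± 3 days", so the window is attached to Day 14 and Day 7 has none. The copy of that table in SAP Appendix 1 is the same.

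**Analysis windows.** SAP Table 3-3 ("Analysis Visit Windows for SARS-CoV-2 Viral Load in Parts A and B") assigns samples by study day: Day 5 is Study Days 5 to 6, Day 7 is 7 to 9, and Day 14 is 10 to 21. Tables 3-1 (vital signs and SpO₂) and 3-5 (safety labs) use the same limits for these three visits. For Part C viral load, Table 3-4 has the same Day 5 and Day 7 windows.

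**Choosing among records in one window.** SAP 3.8.3 takes the record closest to the nominal day, "with the exception of viral load in which the latest record will be selected". The primary endpoint has its own rule in the same section: "All values from different days within an analysis window will be used for DAVG calculation". SAP 6.1.1 runs DAVG7 "through the last available value up to Study Day 7".

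**The concern.** Day 7 closes the primary endpoint period, and the changes in viral load to Day 5 and to Day 7 are named secondary endpoints. A site that reads 6.4 as ± 3 days around Day 7 would think Days 4 to 10 acceptable, while a site working from the schedule table would not. Protocol 6.8 attaches a separate window to each of its two visit days, so the single shared parenthesis in 6.4 leaves real doubt.

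The SAP rule matters whichever reading was meant, because SAP 3.8.2 itself expects visits to miss their scheduled days. For viral load only, the plan sets aside closeness to the nominal day, so a sample taken exactly on Day 5 can be discarded for one taken a day later. A single Day 6 visit then alters one secondary endpoint value and removes another, in arms of about 12.

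**Working it through.** **Step 1. Place the Day 7 visit on each of Study Days 4 to 10.** Keep the other visits on schedule, then apply Table 3-3 and SAP 3.8.3.

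| Day 7 visit held on | Viral load window | Day 5 value used | Day 7 value |
|---|---|---|---|
| Day 4 | Day 4 | Day 5 swab | missing |
| Day 5 | Day 5 | later of the two Day 5 swabs | missing |
| Day 6 | Day 5 | **Day 6 swab** | missing |
| Days 7, 8, 9 | Day 7 | Day 5 swab | present |
| Day 10 | Day 14 | Day 5 swab | missing |

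On the wide reading of 6.4, 3 of the 7 dates reach the SAP Day 7 window. Days 4 and 5 are already dosing and swab visits, so Days 6 and 10 are the realistic misses. With a Day 10 visit, an on-time Day 14 swab is selected for Day 14; if Day 14 is missed, the Day 10 swab is reported there.

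**Step 2. Labs and vital signs.** The closest-record rule applies. For a Day 6 visit, the Day 5 record is 0 days from nominal and the Day 6 record is 1 day away, so Day 5 is kept. Only the Day 7 value leaves its column.

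**Step 3. DAVG7.** Assume a linear decline of s log10 per day from Day 1, with swabs on Days 2 to 5 plus the Day 7 visit. The trapezoidal average of a straight line is its value at the midpoint of the first and last times used.

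- Day 7 swab: midpoint of 2 and 7 is 4.5, giving −3.5s
- Day 6 swab: midpoint of 2 and 6 is 4, giving −3s
- Day 10 swab (not used, curve ends at Day 5): midpoint of 2 and 5 is 3.5, giving −2.5s

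| Day 7 visit on | s = 0.2 | s = 0.3 | s = 0.5 |
|---|---|---|---|
| Day 7 | −0.70 | −1.05 | −1.75 |
| Day 6 | −0.60 | −0.90 | −1.50 |
| Day 10 | −0.50 | −0.75 | −1.25 |

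The slopes are assumptions; the documents give none. A Day 6 swab is kept alongside Day 5, but a Day 10 swab is lost. (Days 8 and 9 lie inside the SAP Day 7 window but beyond the Study Day 7 limit of DAVG7, so their use there is unclear.)

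**Step 4. By-visit summaries.** Part A and Part B each randomize about 36 participants 1:1:1, so 36/3 = 12 per arm. Assume 10 to 25% of Day 7 visits fall on Day 6 or Day 10, unrelated to outcome.

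- Day 7 values kept: 12 × 0.90 = 10.8 to 12 × 0.75 = 9
- Standard error ratio: 1/√0.90 = 1.05 to √(12/9) = 1.15
- Shift in one participant's Day 5 change from a Day 6 visit: one extra day of decline, −0.3 log10 at s = 0.3 (−0.2 to −0.5)
- Shift in the arm mean if all those visits were on Day 6: 0.10 × 0.3 = 0.03 to 0.25 × 0.3 = 0.075 log10

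**The case against.** The strongest reply is that there may be no conflict in the protocol. The parenthesis in 6.4 stands directly after 14, and both copies of the schedule table attach ± 3 days to Day 14 alone. A ± 3 day window on Day 7 would reach back to Days 4 and 5, which are already visits "completed daily and prior to study treatment administration from Days 2-5 in-clinic". A reader might infer that 6.4 plainly permits Days 4 to 10, so that a fully compliant visit loses its data. The documents do not support that as settled: on the narrower reading, text and tables agree and such visits are simply off schedule. That part of the reply stands, and the text is ambiguous rather than shown to be contradictory.

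Two other inferences go too far:

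- **That any off-day visit overwrites Day 5.** Days 4 and 10 cannot. In practice only Day 6 does, and only for viral load.
- **That the primary endpoint or safety review is compromised.** DAVG7 uses values from all days, so a Day 6 value is kept, and SAP 6.1.1 defines DAVG7 when data stop before Day 7. Treatment-emergent lab abnormalities count at any postbaseline time up to 30 days after the last dose (SAP 7.2.2.1), so an abnormality found at a displaced visit still counts.

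It is also fair that the by-visit viral load changes are descriptive, that individual values are listed, and that SAP 6.1.3 applies no DAVG7 test within Part A or Part B.

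The reply does not dispose of the selection rule, which acts in the same way on either reading of 6.4. Nor are Parts A and B wholly descriptive, since their DAVG7 values enter the pooled ANCOVA if the parts are judged poolable (SAP 3.2 and 6.1.3).

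**Conclusion.** The point holds in two limited parts. First, Protocol 6.4 and Appendix Table 1 do not give one unambiguous Day 7 window for Parts A and B, and they must be reconciled with each other and with the SAP. Second, under the SAP as written, a Day 7 visit on Day 6 replaces an on-schedule Day 5 swab in the change-to-Day-5 summary and empties Day 7; the same can happen in Part C. In Parts A and B a Day 10 visit empties Day 7 and contributes nothing to DAVG7.

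The effect is modest. The 5 to 15% rise in the Day 7 standard error, and the arm-mean shift of 0.03 to 0.075 log10 at Day 5, rest on an assumed 10 to 25% off-day rate; the shift also rests on an assumed 0.3 log10 per day. If off-day visits are equally common in all arms and decline is similar, comparisons between arms move less than the arm means do. It is still worth correcting: the visit closes the primary endpoint period, and a stated rule discards a sample taken exactly on its nominal day.

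**What to change.** 1. State one Day 7 visit window in Protocol 6.4 and Appendix Table 1 (both copies), and align SAP Tables 3-1, 3-3 and 3-5 with it. Which window applies is for the sponsor to decide. If it admits Day 6, the SAP Day 7 windows need to start there and the Day 5 windows need to end on Day 5.
2. In SAP 3.8.3, drop the latest-record exception for by-visit viral load, so that the record closest to the nominal day is used as for other measures. A Day 5 swab then cannot be displaced by a Day 6 swab in any part. The separate DAVG7 rule can stay.

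The second change protects the Day 5 value but does not restore a Day 7 value for a Day 6 or Day 10 visit; that depends on the first. The cost is a clarifying line in the protocol, a short SAP edit and a small programming change.

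Assigning samples by eCRF visit label within the protocol window is not needed. It would change nothing for a Day 6 visit if Day 7 has no window. If the window were ± 3 days, it could report a Day 4 or Day 10 swab as Day 7, a shift of 3 × 0.3 = 0.9 log10 at the assumed slope.

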6.5. Study Parts A and B: Day 28 Follow-Up Assessment (\pm 5 days)

The following evaluations are to be completed on Day 28 and may be completed by telephone:

- Review AEs and concomitant medications

6.6. Study Part C: Baseline/Day 1, Days 3, 5, and 7 Assessments

The investigator must have confirmed eligibility before proceeding with randomization. If the screening and Day 1 visits occur on the same day, no procedures need to be repeated. Whenever possible, Day 1 dosing should occur on the same day as screening. The following evaluations are to be completed at Days 1, 3, 5, and 7. They may be completed at home with the assistance of home nursing. Participants must complete the following assessments before being administered study treatment, unless otherwise stated:

- Complete symptom-directed physical examination including vital signs (heart rate, temperature, blood pressure, SpO₂)
- Complete daily adapted FLU-PRO[©] questionnaire
- On Days 1 through 5, perform FEV₁ (predose and 10 minutes postdose)

Repeat of FEV₁ should be performed 30 minutes postdose if there is > 15% reduction in FEV₁ at 10 minutes postdose compared with the same day predose FEV₁. FEV₁ assessment may also be performed if there is a clinical concern of bronchospasm

- Obtain nasopharyngeal and oropharyngeal swabs, and saliva samples for SARS-CoV-2 RT-qPCR testing and possible viral resistance testing
- PK assessments

Days 3 and 5: Sparse plasma PK assessment at predose

Day 7: Single anytime plasma PK assessment

- Safety laboratory samples (Days 1, 3, 5, and 7)
- Review AEs and concomitant medications
- Remdesivir for Inhalation Solution formulation administration (Days 1-5):

Remdesivir for Inhalation Solution formulation may be administered at home to participants with in-person or telehealth support

For participants with pre-existing pulmonary conditions (ie, chronic obstructive pulmonary disease [COPD] or asthma) enrolled in Part C of the study, prescribed inhalers may not be used \leq 30 minutes prior to Remdesivir for Inhalation Solution formulation administration

Healthcare professionals overseeing Remdesivir for Inhalation Solution formulation therapy remotely will observe the patient for any signs of adverse event. If any adverse event is observed and cannot be managed remotely appropriate urgent care measures will be implemented.

- Approximately 30 minutes after dose administration, participants should be observed remotely prior to telehealth support session concluding

6.7. Study Part C: Days 2 and 4 Assessments

The following evaluations are to be completed daily and prior to study treatment administration on Days 2 and 4. They may be completed at home with telehealth support, unless otherwise stated:

- Complete daily adapted FLU-PRO[©] questionnaire
- Perform FEV₁ (predose and 10 minutes postdose)

Repeat of FEV₁ should be performed 30 minutes postdose if there is > 15% reduction in FEV₁ at 10 minutes postdose compared with the same day predose FEV₁. FEV₁ assessment may also be performed if there is a clinical concern of bronchospasm

- Review AEs and concomitant medications
- Remdesivir for Inhalation Solution formulation administration:

Remdesivir for Inhalation Solution formulation may be administered at home to participants with in-person or telehealth support

For participants with pre-existing pulmonary conditions (ie, COPD or asthma) enrolled in Part C of the study, prescribed inhalers may not be used ≤ 30 minutes prior Remdesivir for Inhalation Solution formulation administration

Healthcare professionals overseeing Remdesivir for Inhalation Solution formulation therapy remotely will observe the patient for any signs of adverse event. If any adverse event is observed and cannot be managed remotely appropriate urgent care measures will be implemented.

- Approximately 30 minutes after dose administration, participants should be observed remotely prior to telehealth support session concluding

